### **7.3 LOST TO FOLLOW UP**

A participant will be considered lost to follow-up if he or she repeatedly fails to return for scheduled visits and is unable to be contacted by the study site.

The following actions must be taken if a participant fails to return to the clinic for a required study visit:

- The site must attempt to contact the participant and reschedule the missed visit as soon as possible and counsel the participant on the importance of maintaining the assigned visit schedule and ascertain whether or not the participant wishes to and/or should continue in the study.
- Before a participant is deemed lost to follow up, the Investigator or designee must make every effort to regain contact with the participant (where possible, 3 telephone calls and, if necessary, a certified letter to the participant's last known mailing address or local equivalent methods). These contact attempts should be documented in the participant's medical record.
- Should the participant continue to be unreachable, he/she will be considered to have withdrawn from the study.
- Discontinuation of specific sites or of the study as a whole are handled as part of [Section 10.1](#).

## 8 STUDY ASSESSMENTS AND PROCEDURES

- Study procedures and their timing are summarized in the SoA (see [Section 1.3](#)). Protocol waivers or exemptions are not allowed.
- Adherence to the study design requirements, including those specified in the SoA (see [Section 1.3](#)), is essential and required for study conduct.
- All screening evaluations must be completed and reviewed to confirm that potential participants meet all eligibility criteria. The Investigator will maintain a screening log to record details of all participants screened and to confirm eligibility or record reasons for screening failure, as applicable.
- Procedures conducted as part of the participant's routine clinical management (eg, blood count) and obtained before signing of the ICF may be utilized for screening or baseline purposes provided the procedures met the protocol-specified criteria and were performed within the time frame defined in the SoA (see [Section 1.3](#)).
- Patient-Reported Outcome questionnaires including NRS should be completed by the participants before the consultation and/or clinical tests, in a quiet place. The questionnaires should be completed by the participants themselves, independently from their physician, the study nurse or any other medical personnel and without any help from friends or relatives.
- In light of the public health emergency related to Coronavirus disease 2019 (COVID-19) (or in case of any other pandemic requiring public health emergency), the continuity of clinical study conduct and oversight may require implementation of temporary or alternative mechanisms eg, phone contact, virtual visits, online meetings, use of local clinic or laboratory locations, and home visits by skilled staff. Implementation of such mechanisms may differ country by country, depending on country regulations and local business continuity plans. Additionally, no waivers to deviate from protocol enrollment criteria due to COVID-19 (or any other pandemic) will be granted. All temporary mechanisms utilized, and deviations from planned study procedures are to be documented as being related to COVID-19 (or any other pandemic) and will remain in effect only for the duration of the public health emergency.

### 8.1 EFFICACY ASSESSMENTS

Efficacy data will be collected via electronic devices.

The e-diary is used for daily recording of participant's answers to the WI-NRS, pain-NRS, and sleep-NRS questionnaires. This device will be dispensed at screening visit (Visit 1), including instructions for use. Participants will be instructed on the use of the device.

Recorded information will be downloaded from this device daily. At EOS Visit, the e-diary will be downloaded and returned to the site.

On regular basis, the site staff should review on vendor's website the information downloaded from participants' e-diary. They should particularly check status of the disease reviewing

WI-NRS, as well as compliance to background therapy and overall e-diary compliance. The site should follow up with the participant as appropriate.

Participants will fill in the DLQI, HADS, EQ-5D-5L, PGIC, PGIS, and missed school/work days questionnaires during their site visit on a tablet that will be provided to the site. This device is kept at the site during the study.

### **8.1.1 Worst-itch numeric rating scale**

Worst-itch numerical rating scale (WI-NRS) is a PRO comprised of a single item rated on a scale from 0 (“No itch”) to 10 (“Worst imaginable itch”). Participants are asked to rate the intensity of their worst pruritus (itch) over the past 24 hours using this scale.

Participants will complete the WI-NRS daily according to the SoA (see [Section 1.3](#)). The assessment tool is provided in [Section 10.7.1](#).

### **8.1.2 Investigator's global assessment for prurigo nodularis**

Investigator's global assessment for prurigo nodularis (IGA PN) is a clinician-reported outcome (ClinRO) that allows clinicians to assess the activity of PN (IGA PN-A) using a 5-point scale from 0 (clear) to 4 (severe); and the stage of the disease (IGA PN-S) using a 5-point scale from 0 (clear) to 4 (severe).

Clinicians will complete the IGA PN as described in the SoA (see [Section 1.3](#)). The assessment tool is provided in [Section 10.7.2](#).

### **8.1.3 Prurigo activity score**

The PAS is a ClinRO measurement. The original PAS questionnaire Version 0.9 consists of 7 items, developed by expert clinicians in PN ([25](#)). The items of the PAS evaluate the pruriginous lesions in terms of:

- Type (visible lesions: Item 1a; predominant lesions: Item 1b);
- Estimated number (Item 2);
- Distribution (Item 3, 4);
- Size (biggest lesion: Item 6a; representative lesion: Item 6b).

Other items evaluate the representative body area and exact number of lesions (Item 5), the activity in terms of percentage of pruriginous lesions with excoriations/crusts on top (reflecting active scratching; Item 7a) and the percentage of healed pruriginous lesions (reflecting healing of chronic prurigo; Item 7b).

A 5-item simplified version of the PAS will be used in the current study. In particular, Item 3 (lesion distribution) and Item 6 (lesion monitoring) of the original PAS were removed, and the response options slightly modified and refined.

Clinicians will complete the screening/baseline version at screening and baseline visits, and will complete the follow-up version of the modified PAS at the other visits, as reported in the SoA (see [Section 1.3](#)). The assessment tool is provided in [Section 10.7.3](#).

#### **8.1.4 Dermatology life quality index**

The DLQI is a PRO developed to measure dermatology-specific HRQoL in adult patients ([27](#)). The instrument comprises 10 items assessing the impact of skin disease on patients' HRQoL over the previous week. The items cover symptoms, leisure activities, work/school or holiday time, personal relationships including intimate, the side effects of treatment, and emotional reactions to having a skin disease. It is a validated questionnaire used in clinical practice and clinical trials ([26](#)). Response scale is a 4-point Likert scale (0 = "not at all" and 3 = "very much") for nine items. The remaining one item about work/studying asks whether work/study has been prevented and then (if "No") to what degree the skin condition has been a problem at work/study; the item is rated on a 3-point Likert scale ("Not at all" to "A lot"). Overall scoring ranges from 0 to 30, with a high score indicative of a poor HRQoL.

Participants will complete the questionnaire at time points according to SoA (see [Section 1.3](#)). The assessment tool is provided in [Section 10.7.4](#).

#### **8.1.5 Pain and sleep numeric rating scales**

Participants will be asked to rate their worst skin pain in the past 24 hours using a 0 to 10 NRS, with 0 = No pain to 10 = Worst pain possible.

In addition, participants will be asked to rate their sleep quality on their past night upon awakening, using a 0 to 10 NRS, with 0 = Worst possible sleep and 10 = Best possible sleep.

Participants will complete the skin pain NRS and sleep quality NRS once a day.

The assessment tools are provided in [Section 10.7.7](#) and [Section 10.7.8](#).

#### **8.1.6 Hospital anxiety and depression scale**

The HADS is a PRO instrument for screening anxiety and depression in non-psychiatric populations; repeated administration also provides information about changes to a patient's emotional state ([28, 29](#)). The HADS consists of 14 items, 7 each for anxiety and depression symptoms; possible scores range from 0 to 21 for each subscale. The following cut-off scores are recommended for both subscales:

- 0 to 7: normal
- 8 to 10: borderline abnormal (borderline case)
- 11 to 21: abnormal

Participants will complete the questionnaire as described in the SoA (see [Section 1.3](#)). The assessment tool is provided in [Section 10.7.5](#).

### **8.1.7 Patient Global Impression of Change of disease and Patient Global Impression of Severity**

The PGIC is a one-item questionnaire that asks patients to provide the overall self-assessment of change in their PN overall on a 7-point scale, compared to just before patient started taking the study injection. Response choices are: 0 = “Very much better”, 1 = “Moderately better”, 2 = “A little better”, 3 = “No change”, 4 = “A little worse”, 5 = “Moderately worse”, 6 = “Very much worse”.

The PGIS is a one-item questionnaire that asks patients to provide the overall self-assessment of their disease severity on a 4-point scale for the past week. Response choices are: 1 = “none”, 2 = “Mild”, 3 = “Moderate”, 4 = “Severe”.

Participants will complete the 2 items as described in the SoA (see [Section 1.3](#)). The items are provided in [Section 10.7.9](#) and [Section 10.7.10](#).

### **8.1.8 Euroqol 5 dimensions questionnaire**

The Euroqol-5 dimensions (EQ-5D) is a standardized PRO measure of health status developed by the EuroQOL Group in order to provide a simple, generic measure of health for clinical and economic appraisal ([30](#)). The EQ-5D consists of 2 parts: the descriptive system and the EQ visual analog scale (VAS). The EQ-5D descriptive system comprises the following 5 dimensions: mobility, self-care, usual activities, pain/discomfort, and anxiety/depression. Each dimension has 5 levels of perceived problems: “no problem”, “slight problems”, “moderate problems”, “severe problems” and “inability to do the activity”. The respondent is asked to indicate his/her health state by ticking (or placing a cross) in the box against the most appropriate statement in each of the 5 dimensions; this results in a 1-digit number expressing the level for that dimension. The digits for 5 dimensions can be combined in a 5-digit number describing the respondent’s health state. The EQ VAS records the respondent’s self-rated health on a vertical VAS where the endpoints are labeled “best imaginable health state (100)” and “worst imaginable health state (0)”. This information can be used as a quantitative measure of health outcome as judged by the individual respondents.

Participants will complete the questionnaire as described in the SoA (see [Section 1.3](#)). The assessment tool is provided in [Section 10.7.6](#).

### **8.1.9 Missed school/work days**

Participants who are employed or enrolled in school will be asked to report the number of sick leave/missed school days since the last study assessment.

Participants will complete the questionnaire as described in the SoA (see [Section 1.3](#)). The assessment tool is provided in [Section 10.7.11](#).

## 8.2 SAFETY ASSESSMENTS

Planned time points for all safety assessments are provided in the SoA (see [Section 1.3](#)).

### 8.2.1 Physical examinations

- A complete physical examination will include, at a minimum, assessments of the skin (full body skin exam), nasal cavities, eyes, ears, respiratory, cardiovascular, gastrointestinal, neurological, lymphatic, and musculoskeletal systems.
- Participants must be disrobed and provided with a hospital gown before the skin examination.
- Investigators should pay special attention to clinical signs related to previous serious illnesses.
- Any new finding or worsening of previous finding should be reported as a new AE.

### 8.2.2 Vital signs

- Vital signs will be measured in a semi-supine or sitting position after 5 minutes rest and will include body temperature, SBP and DBP, and pulse and respiratory rate. Blood pressure and pulse measurements should be assessed using the same arm with a completely automated device. Manual techniques will be used only if an automated device is not available.
- Body weight (kg) will be measured at screening (Visit 1), EOT, and EOS visits. Height will be measured at screening visit (Visit 1). Height and weight should be measured with indoor clothing but without shoes.

### 8.2.3 Electrocardiograms

- Single 12-lead ECG will be obtained as outlined in the SoA (see [Section 1.3](#)) using an ECG machine that automatically calculates the heart rate and measures PR, QRS, QT, and QTcF intervals. Refer to [Section 7](#) for QTcF withdrawal criteria and any additional QTcF readings that may be necessary. The ECG should be recorded after 10 minutes of rest in the supine position.

### 8.2.4 Clinical safety laboratory assessments

- See Appendix 2 ([Section 10.2](#)) for the list of clinical laboratory tests to be performed and to the SoA (see [Section 1.3](#)) for the timing and frequency.
- The Investigator must review the laboratory report, document this review, and record any clinically relevant changes occurring during the study in the AE section of the CRF. The laboratory reports must be filed with the source documents. Clinically significant abnormal laboratory findings are those which are not associated with the underlying disease, unless judged by the Investigator to be more severe than expected for the participant's condition.
- All laboratory tests with values considered clinically significantly abnormal during participation in the study or within 12 weeks after the last dose of study intervention

should be repeated until the values return to normal or baseline or are no longer considered clinically significant by the Investigator or medical monitor.

- If such values do not return to normal/baseline within a period of time judged reasonable by the Investigator, the etiology should be identified and the Sponsor notified.
- All protocol-required laboratory assessments, as defined in Appendix 2 ([Section 10.2](#)), must be conducted in accordance with the laboratory manual and the SoA (see [Section 1.3](#)).
- If laboratory values from non-protocol specified laboratory assessments performed at the institution's local laboratory require a change in participant management or are considered clinically significant by the Investigator (eg, SAE or AE or dose modification), then the results must be recorded in the CRF.

### **8.3 ADVERSE EVENTS AND SERIOUS ADVERSE EVENTS**

#### **Adverse event of special interest**

An AESI is an AE (serious or nonserious) of scientific and medical concern specific to the Sponsor's product or program, for which ongoing monitoring and immediate notification by the Investigator to the Sponsor is required. Such events may require further investigation in order to characterize and understand them. Adverse events of special interest may be added, modified or removed during a study by protocol amendment.

For these AESIs, the Sponsor will be informed immediately (ie, within 24 hours), per SAE notification described in [Section 10.3](#), even if not fulfilling a seriousness criterion, using the corresponding pages in the CRF (to be sent) or screens in the eCRF. If an SAE or any AESI of anaphylactic reactions or systemic allergic reactions that are related to IMP and require treatment, or severe injection site reactions lasting longer than 24 hours, occurs in a participant, blood samples should be collected for determination of functional dupilumab concentration, and ADA assessment at or near the onset and completion of the occurrence of the event, if possible.

- Anaphylactic reactions
- Systemic hypersensitivity reactions
- Helminthic infections
- Any severe type of conjunctivitis or blepharitis
- Keratitis
- Clinically symptomatic eosinophilia (or eosinophilia associated with clinical symptoms)
- Pregnancy of a female subject entered in a study as well as pregnancy occurring in a female partner of a male subject entered in a study with IMP/NIMP;
- Pregnancy occurring in a female participant entered in the clinical trial or in a female partner of a male participant entered in the clinical trial. It will be qualified as an SAE only if it fulfills one of the seriousness criteria.

- In the event of pregnancy in a female participant, IMP should be discontinued.
- Follow-up of the pregnancy in a female participant or in a female partner of a male participant is mandatory until the outcome has been determined.
- Abnormal pregnancy outcomes (eg, spontaneous abortion, fetal death, stillbirth, congenital anomalies, ectopic pregnancy) are considered SAEs.
- Significant ALT elevation
  - ALT  $>5$  x ULN in participants with baseline ALT  $\leq 2$  x ULN;  
OR
  - ALT  $>8$  x ULN if baseline ALT  $>2$  x ULN
- Symptomatic overdose (serious or nonserious) with IMP/NIMP
  - An overdose (accidental or intentional) with the IMP is an event suspected by the Investigator or spontaneously notified by the participant and defined as at least twice the intended dose during an interval of less than 11 days. The circumstances (ie, accidental or intentional) should be clearly specified in the verbatim and symptoms, if any, entered on separate AE forms.
  - An overdose (accidental or intentional) with any NIMP is an event suspected by the Investigator or spontaneously notified by the participant and defined as at least twice the maximum prescribed daily dose, within the intended therapeutic interval. The circumstances (ie, accidental or intentional) should be clearly specified in the overdose form.

The definitions of an AE or SAE can be found in Appendix 3 ([Section 10.3](#)).

Adverse events will be reported by the participant (or, when appropriate, by a caregiver, surrogate, or the participant's legally authorized representative).

The Investigator and any qualified designees are responsible for detecting, documenting, and recording events that meet the definition of an AE or SAE and remain responsible for following up AEs that are serious, considered related to the study intervention or study procedures, or that caused the participant to discontinue the study intervention (see [Section 7](#)).

### **8.3.1 Time period and frequency for collecting AE and SAE information**

All AEs, serious or nonserious, will be collected from the signing of the ICF until the EOS visit at the time points specified in the SoA ([Section 1.3](#)).

All SAEs and AESI will be recorded and reported to the Sponsor or designee immediately and under no circumstance should this exceed 24 hours, as indicated in Appendix 3 ([Section 10.3](#)). The Investigator will submit any updated SAE data to the Sponsor within 24 hours of it being available.

Investigators are not obligated to actively seek AE or SAE after conclusion of the study participation. However, if the Investigator learns of any SAE, including a death, at any time after a participant has been discharged from the study, and he/she considers the event to be reasonably related to the study intervention or study participation, the Investigator must promptly notify the Sponsor.

### **8.3.2 Method of detecting AEs and SAEs**

The method of recording, evaluating, and assessing causality of AE and SAE and the procedures for completing and transmitting SAE reports are provided in Appendix 3 ([Section 10.3](#)).

Care will be taken not to introduce bias when detecting AEs and/or SAEs. Open-ended and non-leading verbal questioning of the participant is the preferred method to inquire about AE occurrences.

### **8.3.3 Follow-up of AEs and SAEs**

After the initial AE/AESI/SAE report, the Investigator is required to proactively follow each participant at subsequent visits/contacts. At the pre-specified study end-date, all SAEs and nonserious AESI (as defined in [Section 8.3](#)) will be followed until resolution, stabilization, the event is otherwise explained, or the participant is lost to follow-up (as defined in [Section 7.3](#)). Further information on follow-up procedures is given in Appendix 3 ([Section 10.3](#)).

### **8.3.4 Regulatory reporting requirements for SAEs**

- Prompt notification by the Investigator to the Sponsor of a SAE is essential so that legal obligations and ethical responsibilities towards the safety of participants and the safety of a study intervention under clinical investigation are met.
- The Sponsor has a legal responsibility to notify both the local regulatory authority and other regulatory agencies about the safety of a study intervention under clinical investigation. The Sponsor will comply with country-specific regulatory requirements relating to safety reporting to the regulatory authority, Institutional Review Boards (IRB)/Independent Ethics Committees (IEC), and Investigators.
- Investigator safety reports must be prepared for suspected unexpected serious adverse reactions (SUSAR) according to local regulatory requirements and Sponsor policy and forwarded to Investigators as necessary.
- Adverse events that are considered expected will be specified in the reference safety information.
- An Investigator who receives an Investigator safety report describing a SAE or other specific safety information (eg, summary or listing of SAEs) from the Sponsor will review and then file it along with the IB and will notify the IRB/IEC, if appropriate according to local requirements.

### **8.3.5 Pregnancy**

- Details of all pregnancies in female participants and female partners of male participants will be collected after the start of study intervention and until the outcome has been determined.

- If a pregnancy is reported, the Investigator should inform the Sponsor within 24 hours of learning of the pregnancy and should follow the procedures outlined in Appendix 4 ([Section 10.4](#)).
- Abnormal pregnancy outcomes (eg, spontaneous abortion, fetal death, stillbirth, congenital anomalies, ectopic pregnancy) are considered SAEs.

### **8.3.6 Guidelines for reporting product complaints**

Any defect in the IMP/NIMP/device must be reported as soon as possible by the Investigator to the monitoring team that will complete a product complaint form within required timelines.

Appropriate information (eg, samples, labels or documents like pictures or photocopies) related to product identification and to the potential deficiencies may need to be gathered. The Investigator will assess whether or not the quality issue has to be reported together with an AE or SAE.

## **8.4 TREATMENT OF OVERDOSE**

Overdose is an AESI (defined in [Section 8.3](#)). No antidote is available for dupilumab. Sponsor does not recommend specific treatment for an overdose.

In the event of an overdose, the Investigator/treating physician should:

1. Provide symptomatic care.
2. Contact the Medical Monitor immediately.
3. Closely monitor the participant for any AE/SAE and laboratory abnormalities until dupilumab can no longer be detected systemically.
4. Obtain a plasma sample for PK analysis as soon as possible if requested by the Medical Monitor (determined on a case-by-case basis).
5. Document appropriately in the CRF.

Decisions regarding dose interruptions will be made by the Investigator in consultation with the Medical Monitor based on the clinical evaluation of the participant.

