## **8.5 PHARMACOKINETICS**

### **8.5.1 Systemic drug concentration and antidrug antibodies**

#### **8.5.1.1 Sampling time**

Blood samples will be collected for determination of functional dupilumab and anti-dupilumab antibodies in serum as specified in the SoA ([Section 1.3](#)). Special procedures for collection, storage, and shipping of serum are described in separate operational manuals. The date of collection should be recorded in the eCRF.

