**Table 3 - Summary of handling procedures**

Sample type	Functional dupilumab	Anti-dupilumab antibody
Matrix	Serum	Serum
Blood sample volume	5 mL	5 mL
Anticoagulant	None	None
Blood handling procedures	See Operational Manual	See Operational Manual
Serum aliquot split	2 aliquots	2 aliquots
Storage conditions	<6 months: below -20°C <24 months: below -80°C (preferred)	<6 months: below -20°C <24 months: below -80°C (preferred)
Serum shipment condition	In dry ice	In dry ice

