### **8.5.1.3 Bioanalytic method**

Serum PK and ADA samples will be assayed using validated methods as described in [Table 4](#).

Note: In the event of any SAE, any AE of severe injection site reaction lasting longer than 24 hours, or any AESI of anaphylactic reaction or systemic allergic reaction that is related to IMP and require treatment, PK and ADA samples will be collected at or near the onset of the event for any additional analysis if required or for archival purposes. The exact date and time of sample collection must be recorded and entered into the database by the central laboratory. An unscheduled systemic drug concentration page in the eCRF must be completed as well. If necessary for safety monitoring, additional PK and ADA samples may be collected after the EOS Visit until resolution of AE.

Specifically for PK, any changes in the timing or addition of time points for any planned study assessments must be documented and approved by the relevant study team member and then archived in the Sponsor and site study files, but will not constitute a protocol amendment. The IRB/IEC will be informed of any safety issues that require alteration of the safety monitoring scheme or amendment of the ICF.

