ALT: alanine aminotransferase; AST: aspartate aminotransferase; BUN: blood urea nitrogen; DNA: deoxyribonucleic acid; HBc Ab: hepatitis B core antibody; HBs Ab: hepatitis B surface antibody; HBs Ag: hepatitis B surface antigen; HBV: hepatitis B virus; hCG: human chorionic gonadotropin; HCV: hepatitis C virus; HCV Ab: hepatitis C virus antibody; HIV: human immunodeficiency virus; IEC: Independent Ethics Committee; IRB: Institutional Review Board; RBC: red blood cells; RNA: ribonucleic acid; SAE: serious adverse event; SGOT: serum glutamic-oxaloacetic transaminase; SGPT: serum glutamic-pyruvic transaminase; TB: tuberculosis; ULN: upper limit of normal; WBC: white blood cells; WOCBP: woman of childbearing potential

Investigators must document their review of each laboratory safety report.

Laboratory/analyte results that could unblind the study will not be reported to investigative sites or other blinded personnel until the study has been unblinded.

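### Protocol 8.4 asks for a plasma PK sample after an overdose, while every other dupilumab PK provision is for serum and no plasma assay is described

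*Protocol*

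**What the plan says.** Protocol 8.4 lists what the investigator or treating physician does after an overdose. Two items matter here.

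- Item 4: "Obtain a plasma sample for PK analysis as soon as possible if requested by the Medical Monitor". The request is decided case by case.
- Item 3: "Closely monitor the participant for any AE/SAE and laboratory abnormalities until dupilumab can no longer be detected systemically".

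Section 8.5 sets up the concentration measurement. Under 8.5.1.1, "Blood samples will be collected for determination of functional dupilumab and anti-dupilumab antibodies in serum". Table 3 gives the matrix as serum, the anticoagulant as none, and two serum aliquots. Section 8.5.1.3 says: "Serum PK and ADA samples will be assayed using validated methods", and refers to Table 4 for those methods.

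The schedule of activities (1.3) also labels the PK samples as serum. The PK population is defined by serum concentration in both Protocol Table 5 and SAP Table 4.

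A note under Table 9 in Appendix 2 bears on item 3: "Laboratory/analyte results that could unblind the study will not be reported to investigative sites or other blinded personnel until the study has been unblinded".

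**The concern.** Plasma comes from anticoagulated blood. Serum, as Table 3 specifies, comes from blood drawn without anticoagulant. A site that follows 8.4 literally would use a different tube from the one in the PK handling table and produce a matrix for which the protocol describes neither handling nor a dupilumab method.

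At stake is the concentration measurement after a safety event that 8.4 classes as an AESI. The sample is meant to be taken as soon as possible after the event, so it cannot be replaced later if the laboratory finds the matrix unsuitable.

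A smaller question arises on item 3. It ends close monitoring at a state that is normally established by a concentration result, but it does not say who establishes that state, or how, while the trial is blinded.

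**Working it through.** No statistical figure is involved. The check sets the provisions side by side.

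**1. Matrix**

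| Provision | Matrix for dupilumab PK |
|---|---|
| 1.3 Schedule of activities | Serum |
| 8.5.1.1 Sampling time | Serum |
| 8.5.1.2, Table 3 | Serum, no anticoagulant |
| 8.5.1.3 Bioanalytic method | Serum |
| Table 5; SAP Table 4 (PK population) | Serum |
| 8.4 item 4 | Plasma |

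The protocol otherwise collects plasma only as an optional archive sample for biomarker research (1.3, 8.8), not for this assay.

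**2. Does another instruction already produce a serum sample after an overdose?**

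The event-driven samples are set out in footnote f of the schedule, in 8.3 and in 8.5.1.3. The triggers are:
- any SAE;
- a severe injection site reaction lasting more than 24 hours;
- an anaphylactic or systemic allergic reaction that is related to IMP and requires treatment.

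Overdose is not on the list. This gives two cases:
- *The overdose is an SAE or comes with a listed reaction.* A serum sample is called for under Section 8.5, whatever 8.4 says.
- *Any other overdose.* Item 4 is the only event-driven PK instruction, and it names plasma.

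**3. Would the scheduled samples fill the gap?**

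Serum PK samples are planned at Day 1 and Weeks 4, 8, 12, 24 and 36. The longest wait for the next one, ignoring visit windows, is 4 weeks up to Week 12 and 24 − 12 = 12 weeks between Weeks 12 and 24. That does not replace a prompt sample.

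**4. How many samples are affected?**

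Affected samples = overdoses that meet no serum trigger × the share for which the Medical Monitor requests a sample. The documents give neither factor. The result lies between zero and the full number of such overdoses.

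**5. Item 3: is there a basis that needs no concentration result?**

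Section 4.2 bases the 12-week follow-up on the time by which drug is expected to fall below the quantification limit in most patients after the last dose. The last planned dose is at Week 22 and the end-of-study visit at Week 36, so planned follow-up runs 36 − 22 = 14 weeks (98 days) past the last planned dose. An elapsed-time reading of item 3 is therefore possible. However, 8.4 does not refer to 4.2, and no clearance time after an overdose is given.

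**The case against.** The strongest reply is that this is loose terminology. SAP 4.8.1 makes the same slip: it summarises serum concentrations, then calls the placebo value a plasma concentration. On this view a laboratory kit and its manual would settle the tube type, and no second assay was ever intended. Section 8.5.1.3 also lets PK time points be added with documented approval, without an amendment. In addition, the content of Table 4 and the operational manuals cannot be seen here, so the absence of a plasma method cannot be fully verified.

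Most of this can be granted. Loose wording is the likeliest explanation. But item 4 is an instruction that a site acts on, whereas the SAP phrase only sets a value to zero. The permission to add time points does not tell a site which tube to use after an overdose. The sentence introducing Table 4 speaks of serum samples.

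A reader might go further and infer that neither item can be carried out as written. The documents do not support that:
- Plasma can be drawn. What is missing is a described way to handle and assay it.
- Not every overdose is affected by the matrix conflict. The sample depends on a Medical Monitor request, and serious overdoses have a serum route.
- That concentrations are withheld from sites is a reasonable inference from Appendix 2, since a detectable level would be expected to reveal the arm. But the rule is general and does not name dupilumab concentration.
- Item 3 does not require the site to see a concentration, and elapsed time offers a route that needs no code break. The permanent treatment withdrawal that follows a code break at the investigator's request (7.1.1) is therefore not a consequence of 8.4.

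**Conclusion.** The matrix conflict stands. Protocol 8.4 item 4 names plasma where every other dupilumab PK provision names serum, and for an overdose outside the listed serum triggers it is the only event-driven PK instruction. A sample taken as written may not be measurable by the described assay. It is a narrow inconsistency, but more than clerical because it sits in a safety instruction and the sample cannot be retaken.

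Its reach is limited to overdoses for which a sample is requested. Their number is not stated and cannot be estimated from the documents. The efficacy analyses, power and type I error are untouched.

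The conclusion assumes that Table 4 and the operational manuals contain no separate plasma method. If one exists, the defect is a missing cross-reference.

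On item 3, what remains is a missing cross-reference: the section does not say how a blinded site establishes that drug is no longer detectable. That is worth clarifying alongside the main correction but would not justify a comment on its own.

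**What to change.** Reconcile 8.4 item 4 with 8.5 and Table 3 by replacing *plasma sample* with *serum sample, handled as in Table 3*. If a plasma method does exist, cite it in 8.4 and 8.5 instead.

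At the same time, reconcile 8.4 item 3 with 4.2 and Appendix 2, so that it says how the end of monitoring is established under the blind. What that rule should be is for the sponsor's clinical team.

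The stray reference to plasma in SAP 4.8.1 can be corrected at the next SAP revision.

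The cost is two wording changes in the protocol at the next amendment, or by letter to sites, and one word in the SAP. The change of matrix adds no procedure, visit or analysis.
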